Enhancing inhibitory control via non-invasive neurostimulation may improve the efficacy and efficiency of ERP for OCD. The right inferior frontal gyrus (rIFG) is a particularly promising target for such an approach. This region is a key node in neurocircuitry underlying inhibition of a prepotent response. The location of rIFG makes it easily accessible to tDCS, a type of non-invasive neurostimulation delivering a weak electrical current (1-2 mA) via two electrodes placed on the scalp. Neurostimulation via tDCS modulates neuronal excitability by changing membrane potentials and can enhance behavioral plasticity. In healthy individuals, tDCS over rIFG improves inhibitory control of a prepotent response during the SST, a well-established response inhibition paradigm. Such effects have been seen after a single tDCS session, and when stimulation over rIFG was delivered during a course of inhibition training sessions over four days. We propose to extend this approach by coupling tDCS and behavioral training, i.e., ERP, to inhibit compulsive behaviors in OCD.

C. Experimental Method

1. Brief Description of Subjects

For the TIES (Therapy Integrating Exposure and Stimulation) study we will recruit 32 patients with a primary diagnosis of OCD, aged 18-65, with clinically significant OCD symptoms (Y-BOCS total score of ≥ 16). Participants will be naïve to tDCS and will never have completed a minimally adequate trial of ERP (see human subjects section below for additional inclusion/exclusion criteria).

2. Study Design

For this study we will recruit 32 patients with a primary diagnosis of OCD. Each participant will undergo an assessment which will include a structured clinical interview, brief assessments of depression, anxiety, OCD symptoms, and medication and treatment history. Participants will be randomized to one of two combination interventions: Exposure and response prevention (ERP) plus active transcranial direct current stimulation (tDCS) over right inferior frontal gyrus (rIFG) or ERP plus sham tDCS over rIFG. Each group will complete 1 session of psychoeducation and treatment planning, followed by 10 90-minute sessions of their assigned combination intervention. Participants will also complete a post-treatment and one month follow-up assessment.

3. Specific Procedures or Treatments

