"moderately" interfering will be reported to Dr. [Name] by the therapist or evaluator within 24 hours. All other reported side-effects endorsed on the SAFTEE-SI will be discussed with Dr. [Name] during weekly meetings of study staff. Additionally, the following self-report measures will be given at baseline, post-treatment, and 1-month follow-up: the Frost Multidimensional Perfectionism Scale (FMPS), to assess dimensions of perfectionism; the Pathological Obsessive-Compulsive Personality Scale (POPS), to assess current Obsessive Compulsive Personality Disorder; the Obsessional Beliefs Questionnaire (OBQ), to assess dysfunctional beliefs typical of OCD patients; the Intolerance of Uncertainty Scale (IUS), to assess reactions to uncertainty, ambiguous situations, and the future; and the Obsessive-Compulsive Trait Core Dimensions Questionnaire (OC-TCDQ), a measure of harm avoidance and incompleteness. Finally, at the post-treatment assessment, we will use a questionnaire to probe the integrity of the blind.

Measures of Inhibitory Control. Stop-signal task (SST). We will evaluate the impact of active vs sham tDCS plus ERP on a laboratory measure of inhibitory control (Aim 3). Participants will be tested using the SST⁵⁰ at baseline, post-treatment, and 1 month post-treatment. During the SST, participants will see images of either a right- or left-pointing arrow on a computer screen. They develop a prepotent response (based on instruction) to press a button with their right or left index finger, congruent with the direction of the arrow. On a small percent of trials, participants will hear a beep, indicating they should try to stop themselves from pressing the button. The primary outcome variable used to assess inhibitory control is stop-signal reaction time (SSRT), which is the estimated time it takes to inhibit the prepotent response. Visual Analog Scale (VAS). To evaluate the impact of active vs sham tDCS plus ERP on participants' clinical state, we will use a self-report, asking them to rate their ability to resist engaging compulsive behavior during the ERP exercises. Immediately after each ERP exercise, they will rate their experience on a standard VAS, a face-valid assessment of inhibitory control in the clinical context.

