Preliminary and Primary Data Analyses. As the proposed study is a small-sample pilot study, our primary focus will be on examining feasibility, acceptability, and direction of effects. Additionally, all randomized participants will be used in an intent-to-treat analysis. We will use chi-square and t-tests to evaluate any differences between the two conditions at baseline on demographic and other relevant variables, such as initial symptom severity, comorbid depression, or patient adherence to ERP homework. If significant differences exist, we will covary for these variables in our analyses (though we do not anticipate significant group differences at baseline, as urn randomization tends to result in balanced samples.)

Aim 1: Establish feasibility and acceptability of research procedures and clinical intervention.

Hypothesis: Patients with OCD will tolerate this combined ERP + tDCS treatment and will find it acceptable, as determined by rates of retention, treatment completion, and patient report. For Aim 1, we will use chi-square or t-test to compare treatment conditions on rates of retention, session attendance, homework and treatment completion, and patient satisfaction on the CSQ-8.

Aim 2: Gather evidence on preliminary efficacy of tDCS over rIFG as an adjunct to ERP for OCD.

Hypothesis: Patients in the group receiving ERP + active tDCS will show greater reduction in symptom severity over 10 sessions of the combined treatment than those receiving ERP + sham tDCS. For Aim 2, we will use repeated-measures ANOVA with a between-group factor (condition) to evaluate differences in Y-BOCS severity between groups across assessment timepoints. Since this is a small pilot study (N=32), we will also examine group means and direction of effects across all timepoints, not relying solely on statistical approaches which may be underpowered to detect a significant effect.

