Aim 3: Characterize the relationship between measures of inhibitory control and outcome of the combined intervention. Hypotheses: a) Response inhibition, as measured by the SST, will improve more after ERP plus active vs sham tDCS; b) Improvement in OCD severity will correspond to improved inhibitory control on the SST; and c) Patients receiving ERP plus active tDCS will report less difficulty inhibiting compulsions during ERP exercises than those receiving ERP plus sham tDCS. To test our hypotheses for Aim 3, we will: a) use independent measures t-tests to compare change in SSRT from pre- to post-treatment between conditions, and from pre-treatment to follow-up; b) compute a correlation between percent change in Y-BOCS score and percent change in SSRT from baseline to post-treatment, and from baseline to 1-month follow-up, c) use an independent measures t-test to compare self-reported mean difficulty inhibiting compulsions (VAS) during ERP across stimulation conditions.

Revised Data Analysis Plan:

Preliminary and Primary Data Analyses. Given that this study resulted in a smaller than anticipated final sample size, we created a revised analysis plan, appropriate for the smaller sample. Consistent with the original plan for this pilot study, our primary focus will be on examining feasibility, acceptability, and direction of effects. Additionally, all randomized participants will be used in an intent-to-treat analysis. Analyses will focus on descriptive statistics (e.g., means or proportions) with between-group effect sizes calculated, as appropriate.

Aim 1: Establish feasibility and acceptability of research procedures and clinical intervention.

Hypothesis: Patients with OCD will tolerate this combined ERP + tDCS treatment and will find it acceptable, as determined by rates of retention, treatment completion, and patient report. Our primary feasibility outcome of interest is rates of session completion. Our primary acceptability outcome is patient-reported client satisfaction.

Aim 2: Gather evidence on preliminary efficacy of tDCS over rIFG as an adjunct to ERP for OCD.

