Hypothesis: Patients in the group receiving ERP + active tDCS will show greater reduction in symptom severity over 10 sessions of the combined treatment than those receiving ERP + sham tDCS. For Aim 2, we will examine group means on the Y-BOCS and direction of effects at post-treatment, and 1-month follow-up, not relying on statistical approaches which will be underpowered to detect an effect. The Y-BOCS is our primary clinical outcome.

Aim 3: Characterize the relationship between measures of inhibitory control and outcome of the combined intervention. Hypotheses: a) Response inhibition, as measured by the SST, will improve more after ERP plus active vs sham tDCS; b) Improvement in OCD severity will correspond to improved inhibitory control on the SST; and c) Patients receiving ERP plus active tDCS will report less difficulty inhibiting compulsions during ERP exercises than those receiving ERP plus sham tDCS. We regard aim 3 and related hypotheses to be largely exploratory. To investigate our hypotheses for Aim 3, we will: a) calculate mean change in SSRT from pre- to post-treatment, and from pre-treatment to follow-up for both conditions, and between groups effect size; b) compute a correlation between percent change in Y-BOCS score and percent change in SSRT from baseline to post-treatment, and from baseline to 1-month follow-up, c) calculate self-reported mean difficulty inhibiting compulsions (VAS) during ERP and direction of effects across stimulation conditions.

D. Material Inducements

Compensation for participation in assessments will be offered as part of this study. No compensation will be offered for participation in ERP sessions. Participants will receive a payment of \$25 for completing the screening assessment. Participants will participate in a total of 8 additional assessments during the study (baseline, sessions 1, 3, 5, 7, 9, post-treatment, and 1 month follow-up); they will receive payment for completion of each of these assessments (\$30 for the baseline assessment, \$10 for each mid-treatment assessments, \$40 for the baseline assessment, and \$40 for the post-treatment assessment) for maximum compensation of \$185 for completing the screening and all assessments. Participants will have the option to receive payment by check in the mail or Stop & Shop gift card after each assessment.

E. Training of Research Personnel

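### Revised Aim 3(a) leaves baseline SSRT out of its between-group effect size; adding it would modestly improve precision unless the final sample is very small

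*Combined protocol and SAP*

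**What the plan says.** Aim 3(a) in the Revised Data Analysis Plan (section II.C.4) will "calculate mean change in SSRT from pre- to post-treatment, and from pre-treatment to follow-up for both conditions, and between groups effect size". It gives no formula, standardiser or interval for the effect size. The natural reading is that it is computed from the change scores.

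The Original Data Analysis Plan, now superseded, was also unadjusted. It would "use independent measures t-tests to compare change in SSRT from pre- to post-treatment between conditions, and from pre-treatment to follow-up".

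The covariate is already collected. Under Measures of Inhibitory Control (section II.C.3), the stop-signal task is given "at baseline, post-treatment, and 1 month post-treatment". Table 1 marks the first administration in the screening column, which is before treatment either way.

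The nearest provision for adjustment is in the original plan, after tests of baseline differences: "If significant differences exist, we will covary for these variables in our analyses". That rule does not name SSRT and is not repeated in the revised plan. The original plan also relies on the point that "urn randomization tends to result in balanced samples", without naming the balancing variables.

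On size, Study Design says "For this study we will recruit 32 patients with a primary diagnosis of OCD". The revised plan then says "Given that this study resulted in a smaller than anticipated final sample size, we created a revised analysis plan", without giving the final number. The revised plan is descriptive and regards Aim 3 as largely exploratory.

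**The concern.** Taking later SSRT minus baseline SSRT fixes the slope on baseline at 1. If the two standard deviations are equal, the actual slope is rho, which is below 1 for any measure with retest noise. The change score then over-corrects. The arm that happens to start slower tends to show more improvement through regression to the mean, whatever the stimulation does.

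This matters because the revised plan runs no test here and focuses on direction of effects, so the effect size is the between-arm result for the laboratory measure of inhibitory control. Chance baseline differences are also larger in smaller arms, and the revised plan was written because the sample came out smaller than intended.

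**Working it through.** **Inputs.** From the documents: planned N = 32; final N smaller but not stated; SSRT measured before treatment, at post-treatment and at 1 month. The documents give no SSRT standard deviation, no rho, no allocation ratio and no power figure for Aim 3, so there is no figure of the plan's own to reproduce.

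Assumed: equal arms, equal baseline and later SD (set to 1), simple randomisation, rho from 0.3 to 0.8, and total N from 8 to 32.

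**Step 1: variance of each contrast.**
- Change: 2(1-rho) × 4/N.
- Baseline-adjusted: (1-rho²) × (4/N) × (N-3)/(N-4). The last factor is the cost of estimating the slope.
- Ratio, adjusted to change: [(1+rho)/2] × (N-3)/(N-4).

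Example at N=32 and rho 0.5: 0.75 × 29/28 = 0.78.

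**Step 2: 95% half-width in SD units.**
- Change: t(N-2) × √[2(1-rho) × 4/N]. At N=32 and rho 0.5: 2.042 × 0.354 = 0.72.
- Adjusted: t(N-3) × √[(1-rho²) × (4/N) × (N-3)/(N-4)]. At N=32 and rho 0.5: 2.045 × 0.312 = 0.64.

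| Total N | Variance ratio at rho 0.3 / 0.5 / 0.7 / 0.8 | Half-width at rho 0.5, change → adjusted |
|---|---|---|
| 32 | 0.67 / 0.78 / 0.88 / 0.93 | 0.72 → 0.64 |
| 20 | 0.69 / 0.80 / 0.90 / 0.96 | 0.94 → 0.84 |
| 12 | 0.73 / 0.84 / 0.96 / 1.01 | 1.29 → 1.20 |
| 8 | 0.81 / 0.94 / 1.06 / 1.125 | 1.73 → 1.76 |

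At N=8 and rho 0.5 the variance is slightly lower but the interval is slightly wider, because one fewer degree of freedom raises the t quantile from 2.447 to 2.571. At N=12 and rho 0.8 the half-widths are 0.81 and 0.83.

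**Step 3: break-even.** Setting the variance ratio to 1 gives rho = (N-5)/(N-3): 27/29 = 0.93 at N=32, 15/17 = 0.88 at N=20, 7/9 = 0.78 at N=12 and 3/5 = 0.60 at N=8. Above these values, adjustment does not reduce the variance.

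**Step 4: effect of a chance baseline difference.** Given an observed difference D in baseline means, the change contrast moves by -(1-rho)D. The SD of D is √(4/N): 0.354 at N=32 and 0.447 at N=20. At rho 0.5, a one-SE imbalance therefore shifts the change contrast by 0.5 × 0.354 = 0.18 SD at N=32 and 0.5 × 0.447 = 0.22 SD at N=20. Over rho 0.3 to 0.8 the shift runs from 0.25 down to 0.07 SD at N=32, and from 0.31 down to 0.09 SD at N=20.

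**Step 5: simulation check.** With 40,000 replicates per setting, the variance ratios agreed with the formula to within about 0.015. The slope of the change contrast on D was about -0.70, -0.50, -0.30 and -0.20 for the four values of rho. The slope of the adjusted contrast was within 0.01 of zero throughout.

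**The case against.** The strongest reply is that nothing here is an error. The hypothesis is that SSRT improves more with active stimulation, and mean change by arm describes that directly. Over repeated randomisations the change contrast is unbiased. The aim is exploratory, no test or decision rests on it, and the plan does not say how its effect size is to be computed, so reading it as change-based is an inference. All of this stands, and it limits the weight of the point.

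A second reply is that the final sample may be so small that estimating a slope costs more than it returns. This also stands in part. At about 12 patients or fewer with a high rho there is no precision gain and possibly a small loss. At N=20 or more, adjustment is more precise across the assumed range of rho. At any N it removes the dependence on the observed baseline difference.

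A third reply is that urn randomisation or the original covariate rule already deals with imbalance. This carries little weight. The balancing variables are not named, the rule is not carried into the revised plan, and a significance trigger would rarely fire in a sample this small.

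**Conclusion.** The point holds as a modest improvement in precision. Under equal arms, equal SDs and rho of 0.5, the 95% interval narrows by about 11% at N=32 (0.08/0.72) and at N=20 (0.10/0.94), and by about 7% at N=12 (0.09/1.29). There is no gain at N=8. The size rests on rho and on the final N, neither of which the documents give.

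A reader might infer more, in four ways that the documents do not support:
- **That the planned contrast is biased.** It is not, over randomisation. The weakness is extra variance, and a shift conditional on the baseline difference that happens to occur.
- **That the trial loses power.** The t-test belongs to the superseded plan. The revised plan does no test for this aim.
- **That chance imbalance could readily reverse the sign.** For an assumed true effect of 0.8 SD at rho 0.5, imbalance alone would have to be about 4.5 standard errors at N=32 (0.8/0.177) or 3.6 at N=20 (0.8/0.224). Direction is at risk only if the true effect is small, of the order of the 0.18 to 0.22 SD shifts.
- **That the mechanism rests on Aim 3(a) alone.** Aim 3(b) correlates SSRT change with Y-BOCS change, and Aim 3(c) compares self-rated difficulty in resisting compulsions by arm.

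**What to change.** In revised Aim 3(a), keep the mean SSRT changes by arm as descriptives. Define the between-group effect, separately at post-treatment and at 1 month, as the arm coefficient from a linear regression of SSRT at that visit on arm and baseline SSRT. Divide it by the pooled baseline SD and report it with a 95% CI. Adjust whether or not the arms differ at baseline. This also supplies the standardiser and the interval that the plan now lacks.

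The cost is one or two sentences in the plan and one degree of freedom per model. No new data are needed. If the final sample is about 12 or fewer and rho is high, expect no precision gain or a small loss. Reporting the unadjusted mean changes alongside lets the reader see both.

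### Aim 3(b) does not say how treatment arm enters the correlation of Y-BOCS change with SSRT change; a single pooled value mixes a shared tDCS effect with a within-arm link

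*Combined protocol and SAP*

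**What the plan says.** The text is in section II.C.4 (Data Analysis), Revised Data Analysis Plan, Aim 3. The aim is to "Characterize the relationship between measures of inhibitory control and outcome of the combined intervention", and hypothesis (b) reads "Improvement in OCD severity will correspond to improved inhibitory control on the SST". The analysis for (b) is to "compute a correlation between percent change in Y-BOCS score and percent change in SSRT from baseline to post-treatment", with the same correlation from baseline to 1-month follow-up.

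The items on either side of it do mention arm. Item (a) gives mean SSRT change "from pre-treatment to follow-up for both conditions, and between groups effect size". Item (c) is to "calculate self-reported mean difficulty inhibiting compulsions (VAS) during ERP and direction of effects across stimulation conditions". Item (b) has no arm term.

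The Original Data Analysis Plan specifies the same correlation for 3(b) and is equally silent. Its only covariate rule concerns variables that differ between conditions at baseline. Arm is not such a variable, and the revised plan does not repeat the rule.

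The plan limits the weight placed on this aim: "We regard aim 3 and related hypotheses to be largely exploratory".

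**The concern.** Because (a) and (c) refer to the conditions and (b) does not, one correlation over all patients is the natural reading of (b). That is an inference; the text does not settle it.

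On that reading, the trial's own hypotheses create an ambiguity. Aim 2 predicts "Patients in the group receiving ERP + active tDCS will show greater reduction in symptom severity over 10 sessions of the combined treatment" than those on sham, and hypothesis 3(a) predicts "Response inhibition, as measured by the SST, will improve more after ERP plus active vs sham tDCS". If both hold, the active arm sits further along both axes of the scatter than the sham arm. The separation between the two clusters then produces a positive pooled correlation, whether or not patients within an arm who gain more inhibitory control also lose more symptoms.

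Item (b) is the only planned analysis that relates the two changes to each other. The by-arm summaries under Aims 2 and 3(a) show whether each measure moved with arm, but not whether the two changes go together within an arm. A reader could take a positive pooled r as evidence of that second link when it reflects only the first.

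**Working it through.** **Inputs from the documents.** Two randomized arms (Study Design); planned N of 32; a final N described only as smaller than anticipated (Revised Data Analysis Plan); predicted direction of the arm effects on Y-BOCS and SSRT (Aims 2 and 3(a)). The plan states no figure for 3(b), so there is none to reproduce.

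**Assumptions.** The documents give no allocation ratio, final N, arm effects or within-arm correlation. I take 1:1 arms, N = 12 to 31, equal within-arm SDs in the two arms, and a range for the rest.

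**Expected pooled correlation.** Let d1 and d2 be the active-versus-sham differences in the two percent changes, in within-arm SD units, with positive meaning more improvement on active. Let r_w be the within-arm correlation. For 1:1 arms:

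r_pooled = (r_w + d1·d2/4) / √[(1 + d1²/4)(1 + d2²/4)]

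Example with r_w = 0 and d1 = d2 = 0.8: the numerator is 0.64/4 = 0.16 and the denominator is 1 + 0.16 = 1.16, so r_pooled = 0.16/1.16 = 0.138.

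| r_w | (d1, d2) | expected pooled r |
|---|---|---|
| 0 | (0.2, 0.2) | 0.010 |
| 0 | (0.5, 0.5) | 0.059 |
| 0 | (0.8, 0.8) | 0.138 |
| 0 | (1.0, 1.0) | 0.200 |
| 0 | (0.8, 0.3) | 0.055 |
| 0 | (0.8, 0) | 0 |
| 0 | (0.8, −0.3) | −0.055 |
| 0.3 | (0.5, 0.5) | 0.341 |
| 0.3 | (0.8, 0.8) | 0.397 |
| 0.3 | (0.8, 0) | 0.279 |
| 0.5 | (0.8, 0.8) | 0.569 |
| 0.5 | (0.8, 0.2) | 0.499 |
| 0.5 | (0.8, 0) | 0.464 |

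With r_w = 0, the shift needs an arm effect on both measures, and it turns negative if the effects have opposite signs. With a positive r_w, an arm effect on only one measure pulls the pooled r below r_w. With 1:2 arms and r_w = 0, the values at equal d of 0.5, 0.8 and 1.0 are 0.053, 0.125 and 0.182, so the allocation ratio matters little.

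**Sampling error.** The 95% CI half-width around r = 0 is tanh(1.96/√(N−3)) for the pooled value and tanh(1.96/√(N−4)) for the value adjusted for arm.

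| N | pooled | arm-adjusted |
|---|---|---|
| 12 | 0.574 | 0.600 |
| 20 | 0.443 | 0.454 |
| 24 | 0.403 | 0.412 |
| 31 | 0.354 | 0.360 |

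Every shift in the first table is smaller than these half-widths.

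**How far the two values differ in one trial.** Both come from the same patients, so the CI width does not answer this. I simulated 40,000 trials per setting with r_w = 0 and equal arm effects on both measures. The share of trials in which pooled and adjusted r differ by more than 0.1 was:

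| d on both measures | N = 12 | N = 20 | N = 24 | N = 31 |
|---|---|---|---|---|
| 0 | 21% | 8% | 5% | 2% |
| 0.5 | 38% | 29% | 27% | 24% |
| 0.8 | 59% | 60% | 61% | 64% |

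In the same setting the pooled r is positive in about 58% to 79% of trials at d of 0.5 to 0.8, against about 50% for the adjusted r. The two have opposite signs in 22% to 29% of trials at d = 0.8, against 5% to 8% with no arm effects. The mean adjusted r stays within 0.003 of zero.

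**The case against.** The strongest reply is that a pooled correlation answers 3(b) as worded. The hypothesis says that the two improvements correspond; it makes no within-arm or mediation claim. Since (a) and (c) are the arm comparisons, (b) may well be meant as the overall association. The rationale in Specific Aims is also that enhancing inhibition may improve the response to ERP. Covariation that tDCS produces by that route is then part of the relationship of interest, and adjusting for arm removes it. All of this stands, and it is the reason for keeping the pooled value.

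It is also fair that the shift is small and rests on assumed inputs: 0.06 or less for shared effects up to 0.5 SD, and nil if only one measure responds and r_w = 0. The 0.1 threshold in the simulation is arbitrary, and only equal effects were simulated. The revised plan is descriptive, sets no test for 3(b), and reports both measures by arm, so a reader can see when the ambiguity could arise. These points limit the importance of the concern. They do not remove it, because no planned output gives the within-arm association. The revised plan also puts its emphasis on the direction of effects, and the sign of r is what an unstated choice can change.

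Finally, a single partial correlation presumes a similar association in the two arms. If the arms differ, it describes neither well; the plot marked by arm is there to show this.

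**Conclusion.** The concern holds as a minor point. The plan does not say how arm is handled in 3(b). If the arms are pooled, the result cannot separate a shared arm effect from a link among patients given the same treatment. With no within-arm link and equal arm effects of 0.5 to 0.8 SD on both measures, the expected pooled r is 0.06 to 0.14, well within sampling error at any N below 32. These figures depend on assumed effect sizes, 1:1 allocation and N of 12 to 31. The pooled r remains a valid description of overall covariation. The consequence is confined to how one exploratory result is read.

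**What to change.** Keep the pooled correlation, state that it is pooled, and add the arm-adjusted value. Suggested text for Aim 3(b):

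> The correlation of percent change in Y-BOCS with percent change in SSRT will be computed across both arms. Beside it we will report the partial correlation adjusted for arm, with a 95% CI (Fisher z, N−4, where N is the number of patients with both changes), at post-treatment and at 1 month, and a scatter plot marked by arm. Any statement that the two changes go together among patients given the same treatment will rest on the arm-adjusted value.

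This uses data already collected and adds a short passage and one plot per time point. The adjustment costs one degree of freedom, which widens the CI half-width around zero from 0.57 to 0.60 at N = 12 and from 0.35 to 0.36 at N = 31. Neither value will be precise at this sample size, and the report should say so.
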